8.1 TRIAL APPROVAL, SUBJECT INFORMATION, INFORMED CONSENT

This trial will be initiated only after all required legal documentation has been reviewed and approved by the respective Institutional Review Board (IRB / Independent Ethics Committee (IEC and competent authority (CA) according to national and international regulations. The same applies for the implementation of changes introduced by amendments.

Prior to a subject's participation in the trial, written informed consent must be obtained from each subject (or the subject's legally accepted representative) according to ICH-GCP and to the regulatory and legal requirements of the participating country. Each signature must be personally dated by each signatory and the informed consent and any additional subject-information form retained by the investigator as part of the trial records. A signed copy of the informed consent and any additional subject information must be given to each subject or the subject's legally accepted representative.

The subject must be given sufficient time to consider participation in the trial. The investigator or delegate obtains written consent of the subject's own free will with the informed consent form after confirming that the subject understands the contents. The investigator or [REDACTED] delegate must sign (or place a seal on) and date the informed consent form. If a trial collaborator has given a supplementary explanation, the trial collaborator also signs (or places a seal on) and dates the informed consent.

Re-consenting may become necessary when new relevant information becomes available and should be conducted according to the sponsor's instructions.

Proprietary confidential information © 2020 Boehringer Ingelheim International GmbH or one or more of its affiliated companies

The consent and re-consenting process should be properly documented in the source documentation.

For subjects enrolled during the COVID-19 pandemic: In addition to the study specific informed consent, separate written consent will be obtained for testing on SARS-CoV-2 infection.

8.2 DATA QUALITY ASSURANCE

A risk-based approach is used for trial quality management. It is initiated by the assessment of critical data and processes for trial subject protection and reliability of the results as well as identification and assessment of associated risks. An Integrated Quality and Risk Management Plan documents the rationale and strategies for risk management during trial conduct including monitoring approaches, vendor management and other processes focusing on areas of greatest risk.

Continuous risk review and assessment may lead to adjustments in trial conduct, trial design or monitoring approaches.

A quality assurance audit/inspection of this trial may be conducted by the sponsor, sponsor's designees, or by IRB / IEC or by regulatory authorities. The quality assurance auditor will have access to all medical records, the investigator's trial-related files and correspondence, and the informed consent documentation of this clinical trial..

8.3 RECORDS

CRFs for individual subjects will be provided by the sponsor. For drug accountability, refer to Section [4.1.8](#).

ClinBaseTM

In the [REDACTED] – the [REDACTED] – the validated ClinBaseTM system is used for processing information and controlling data collected in clinical studies. In addition to its function as a procedure control system, ClinBaseTM serves as data base. Instead of being entered into CRFs, selected data are directly entered into the system.

8.3.1 Source documents

In accordance with regulatory requirements, the investigator should prepare and maintain adequate and accurate source documents and trial records for each trial subject that include all observations and other data pertinent to the investigation. Source data as well as reported data should follow the 'ALCOA principles' and be attributable, legible, contemporaneous, original, and accurate. Changes to the data should be traceable (audit trail).

Data reported on the CRF must be consistent with the source data or the discrepancies must be explained.

Before providing any copy of subjects' source documents to the sponsor, the investigator must ensure that all subject identifiers (e.g., subject's name, initials, address, phone number,

Proprietary confidential information © 2020 Boehringer Ingelheim International GmbH or one or more of its affiliated companies

and social security number) have properly been removed or redacted to ensure subject confidentiality.

If the subject is not compliant with the protocol, any corrective action (e.g. re-training) must be documented in the subject file.

For the CRF, data must be derived from source documents, for example:

- Subject identification: sex, year of birth (in accordance with local laws and regulations)
- Subject participation in the trial (substance, trial number, subject number, date subject was informed)
- Dates of subject's visits, including dispensing of trial medication
- Medical history (including trial indication and concomitant diseases, if applicable)
- Medication history
- AEs and outcome events (onset date [mandatory], and end date [if available])
- SAEs (onset date [mandatory], and end date [if available])
- Concomitant therapy (start date, changes)
- Originals or copies of laboratory results and other imaging or testing results, with proper documented medical evaluation (in validated electronic format, if available)
- ECG results (original or copies of printouts)
- Completion of subject's participation in the trial (end date; in case of premature discontinuation, document the reason for it, if known)
- Prior to allocation of a subject to a treatment into a clinical trial, there must be documented evidence in the source data (e.g. medical records) that the trial participant meets all inclusion criteria and does not meet any exclusion criteria. The absence of records (either medical records, verbal documented feedback of the subject or testing conducted specific for a protocol) to support inclusion/exclusion criteria does not make the subject eligible for the clinical trial.

Data directly entered into ClinBase™ (that is, without prior written or electronic record) are considered to be source data. The place where data are entered first will be defined in a trial specific Source Data Agreement. The data in ClinBase™ are available for inspection at any time.

8.3.2 Direct access to source data and documents

The investigator /institution will allow site trial-related monitoring, audits, IRB / IEC review and regulatory inspections. Direct access must be provided to the CRF and all source documents/data, including progress notes, copies of laboratory and medical test results, which must be available at all times for review by the Clinical Research Associate, auditor and regulatory inspector (e.g. FDA). They may review all CRFs and informed consents. The accuracy of the data will be verified by direct comparison with the source documents described in section [8.3.1](#). The sponsor will also monitor compliance with the protocol and GCP.

8.3.3 Storage period of records

Trial site:

The trial site(s) must retain the source and essential documents (including ISF) according to the local requirements valid at the time of the end of the trial.

Sponsor:

The sponsor must retain the essential documents according to the sponsor's SOPs.

8.4 EXPEDITED REPORTING OF ADVERSE EVENTS

BI is responsible to fulfil their legal and regulatory reporting obligation in accordance with regulatory requirements.

8.5 STATEMENT OF CONFIDENTIALITY AND SUBJECT PRIVACY

Individual subject data obtained as a result of this trial is considered confidential and disclosure to third parties is prohibited with the exceptions noted in section [8.7](#).

Data protection and data security measures are implemented for the collection, storage and processing of patient data in accordance with the principles 6 and 12 of the WHO GCP handbook.

Personalised treatment data may be given to the subject's personal physician or to other appropriate medical personnel responsible for the subject's welfare. Data generated at the site as a result of the trial need to be available for inspection on request by the participating physicians, the sponsor's representatives, by the IRB / IEC and the regulatory authorities.

8.5.1 Collection, storage and future use of biological samples and corresponding data

Measures are in place to comply with the applicable rules for the collection, biobanking and future use of biological samples and clinical data, in particular

- Sample and data usage has to be in accordance with the separate biobanking informed consent
- The BI-internal facilities storing biological samples from clinical trial participants as well as the external banking facility are qualified for the storage of biological samples collected in clinical trials.
- An appropriate sample and data management system, incl. audit trail for clinical data and samples to identify and destroy such samples according to ICF is in place
- A fit for the purpose documentation (biomarker proposal, analysis plan and report) ensures compliant usage
- A fit for purpose approach will be used for assay/equipment validation depending on the intended use of the biomarker data

Samples and/or data may be transferred to third parties and other countries as specified in the biobanking ICF

8.6 TRIAL MILESTONES

The **start of the trial** is defined as the date of the enrolment of the first subject in the trial.

The **end of the trial** is defined as the ‘date of the last visit of the last subject in whole trial’ (‘Last Subject Completed’) or ‘end date of the last open AE’ or ‘date of the last follow-up test’ or ‘date of an AE has been decided as sufficiently followed-up’, whichever is latest.

Early termination of the trial is defined as the premature termination of the trial for any reason before the end of the trial as specified in this protocol.

Temporary halt of the trial is defined as any unplanned interruption of the trial by the sponsor with the intention to resume it.

Suspension of the trial is defined as an interruption of the trial based on a Health Authority request.

The EC/competent authority in each participating EU member state will be notified about the trial milestones according to the laws of each member state.

A final report of the clinical trial data will be written only after all subjects have completed the trial in all countries (EU or non-EU), so that all data can be incorporated and considered in the report.

The sponsor will submit to the EU database a summary of the final trial results within one year from the end of a clinical trial as a whole, regardless of the country of the last patient (EU or non-EU).

8.7 ADMINISTRATIVE STRUCTURE OF THE TRIAL

The trial is sponsored by Boehringer Ingelheim (BI).

The trial will be conducted at the [REDACTED] [REDACTED], under the supervision of the Principal Investigator. Relevant documentation on the participating (Principal) Investigators (e.g. their curricula vitae) will be filed in the ISF.

BI has appointed a Clinical Trial Leader (CT Leader), responsible for coordinating all required trial activities, in order to

- Manage the trial in accordance with applicable regulations and internal SOPs
- Direct the clinical trial team in the preparation, conduct, and reporting of the trial
- ensure appropriate training and information of local clinical trial managers (CT Managers), Clinical Research Associates, and investigators of participating trial sites

The trial medication will be provided by the [REDACTED] [REDACTED]

Safety laboratory tests will be performed by the local laboratory of the trial site ([REDACTED] [REDACTED]).

Analyses of apremilast concentrations in plasma will be performed under the responsibility of the [REDACTED]

[REDACTED] at suitable contract research organisations.

Proprietary confidential information © 2020 Boehringer Ingelheim International GmbH or one or more of its affiliated companies

On-site monitoring will be performed by BI or a contract research organisation appointed by BI.

Data management and statistical evaluation will be done by BI according to BI SOPs.

Tasks and functions assigned in order to organise, manage, and evaluate the trial are defined according to BI SOPs. A list of responsible persons and relevant local information can be found in the ISF.

10. APPENDICES

Not applicable.

11. DESCRIPTION OF GLOBAL AMENDMENT(S)

11.1 GLOBAL AMENDMENT 1

Date of amendment	16 April 2020
EudraCT number	2019-005037-37
BI Trial number	1407-0041
BI Investigational Medicinal Products	Otezla® (Apremilast) film-coated tablets sourced from two ICH regions (EU and US)
Title of protocol	Bioequivalence of two different tablet formulations of 30 mg of apremilast (EU-sourced Otezla® vs. US-sourced Otezla®) administered in healthy male and female subjects in the fasted state as well as in the fed state (an open-label, randomised, single-dose, four-period, four-sequence crossover study)
To be implemented only after approval of the IRB / IEC / Competent Authorities	
To be implemented immediately in order to eliminate hazard – IRB / IEC / Competent Authority to be notified of change with request for approval	
Can be implemented without IRB / IEC / Competent Authority approval as changes involve logistical or administrative aspects only	
Section to be changed	1) 3.3.4.3 2) 5.2.6.1.4 3) 5.2.6.1.4
Description of change	1) Specification, which of the reasons mandatory lead to discontinuation of the trial. Limitation of severe non-serious adverse events considered as drug-related by the investigator to 25% of the subjects (refer to reason no. 3). 2) Definition of AESIs (depression, mood changes, suicidal ideation, and suicidal behaviour/attempt) 3) BI 730357 was specified as the investigational product whose development could be discontinued (refer to reason no. 5).
Rationale for change	1) Required by Competent Authority and IEC 2) Recommended by Competent Authority and IEC 3) Clarification by Sponsor

Proprietary confidential information © 2020 Boehringer Ingelheim International GmbH or one or more of its affiliated companies

11.2 GLOBAL AMENDMENT 2

Date of amendment	05 November 2020
EudraCT number	2019-005037-37
BI Trial number	1407-0041
BI Investigational Medicinal Products	Otezla® (Apremilast) film-coated tablets sourced from three ICH regions (EU, US, and Japan)
Title of protocol	Bioequivalence of three different tablet formulations of 30 mg of apremilast (EU-sourced Otezla® vs. US-sourced Otezla® vs. Japan-sourced Otezla®) administered in healthy subjects in the fasted state as well as (for EU-sourced Otezla® vs. US-sourced Otezla®) in the fed state (an open-label, randomised, single-dose, five-period, ten-sequence crossover study)

2. LIST OF ABBREVIATIONS

See Medicine Glossary:

<http://glossary>

Term	Definition / description
AESI	Adverse event of special interest
ANOVA	Analysis of variance
AUC _{0-tz}	Area under the concentration-time curve of the analyte in plasma over the time interval from 0 to the last quantifiable data point
AUC _{0-∞}	Area under the concentration-time curve of the analyte in plasma over the time interval from 0 extrapolated to infinity
BMI	Body mass index
CI	Confidence interval
C _{max}	Maximum measured concentration of the analyte in plasma
CSD	Company Standard Displays
CV	Arithmetic coefficient of variation
F/U	Follow Up
gCV	Geometric coefficient of variation
gMean	Geometric mean
Max	Maximum
MedDRA	Medical Dictionary for Regulatory Activities
Min	Minimum
N	Number non-missing observations
P10	10 th percentile
P90	90 th percentile
PKS	PK parameter analysis set
Q1	1 st quartile
Q3	3 rd quartile
RAGe	Report Appendix Generator system
REP	Residual Effect Period
RPM	Report Planning Meeting
SD	Standard deviation
SOC	System organ class
TS	Treated set

Term	Definition / description
WHO-DD	World Health Organization Drug Dictionary

3. INTRODUCTION

As per ICH E9 (1) the purpose of this document is to provide a more technical and detailed elaboration of the principal features of the analysis described in the protocol, and to include detailed procedures for executing the statistical analysis of the primary and secondary variables and other data.

This Trial statistical analysis plan (TSAP) assumes familiarity with the Clinical Trial Protocol (CTP), including Protocol Amendments. In particular, the TSAP is based on the planned analysis specification as written in CTP Section 7 “Statistical Methods and Determination of Sample Size”. Therefore, TSAP readers may consult the CTP for more background information on the study, e.g., on trial objectives, study design and population, treatments, definition of measurements and variables, planning of sample size, randomisation.

Study data (including data entered in the RAVE EDC system and external data provided by suppliers) will be stored in a Clinical Data Repository (CDR).

Pharmacokinetic (PK) parameters will be calculated using Phoenix WinNonlinTM software (version 6.3 or higher, [REDACTED]).

The statistical analyses will be performed within the validated working environment CARE, including SASTM (current Version 9.4, by [REDACTED]), and a number of SASTM-based tools (e.g., macros for the analyses of AE data or laboratory data; Report Appendix Generator system (RAGe) for compilation/formatting of the CTR appendices).

4. CHANGES IN THE PLANNED ANALYSIS OF THE STUDY

The study was prematurely terminated with only 20 of the 40 planned subjects as the development program of BI 730357 had been terminated in all indications, for the treatment of adult patients with plaque psoriasis, axial spondyloarthritis, and psoriatic arthritis.

Consequently, an abbreviated clinical trial report is planned where data on trial subjects, safety, and PK concentrations will be reported. Only descriptive statistics of PK parameters will be provided; no statistical evaluation of PK parameters will be performed.

In addition, the following change compared to the protocol will be made:

In CTP section 7.3 the following was defined: *Important protocol deviation (IPD) categories will be suggested in the TSAP, IPVs will be identified no later than in the Report Planning Meeting, and the IPV categories will be updated as needed.* Due to SOP changes, the IPD categories are no longer suggested in TSAP, but included in an IPD specification file ([3](#)).

5. ENDPOINTS(S)

5.1 PRIMARY ENDPOINT(S)

Section 2.1.2 of the CTP:

The following pharmacokinetic parameters will be determined for apremilast:

- *AUC_{0-tz} (area under the concentration-time curve of the analyte in plasma over the time interval from 0 to the last quantifiable data point)*
- *AUC_{0-∞} (area under the concentration-time curve of the analyte in plasma over the time interval from 0 extrapolated to infinity)*
- *C_{max} (maximum measured concentration of the analyte in plasma)*

[figure not shown]
5.2 SECONDARY ENDPOINT(S)

5.2.1 Key secondary endpoint(s)

This section is not applicable as no key secondary endpoints have been defined in the CTP.

5.2.2 Secondary endpoint(s)

[figure not shown]
This section is not applicable as no secondary endpoints have been defined in the CTP.

Safety and tolerability endpoints

Section 2.2.2.2 of the CTP: Safety and tolerability of apremilast will be assessed based on:

- *Adverse Events (including clinically relevant findings from the physical examination)*
- *Safety laboratory tests*
- *12-lead ECG*
- *Vital signs (blood pressure, pulse rate)*

6. GENERAL ANALYSIS DEFINITIONS

6.1 TREATMENT(S)

For basic study information on investigational products and selection of doses, please see CTP Sections 3 and 4.

The study was to be performed as an open-label, five-period, ten-sequence crossover design. In total, it was planned to assign 40 healthy male and female subjects.

There will be a washout period of at least 5 days between the apremilast administrations.

For details of dosage and formulation see Table 6.1: 1 below:

Table 6.1: 1 Treatments and labels used in the analysis

Treatment	Short label
A Otezla (EU source), 30 mg tablet, qd, fasted	T fasted
B Otezla (US source), 30 mg tablet, qd, fasted	R1 fasted
C Otezla (EU source), 30 mg tablet, qd, fed	T fed
D Otezla (US source), 30 mg tablet, qd, fed	R1 fed
E Otezla (Japan source), 30 mg tablet, qd, fasted	R2 fasted

The study was prematurely stopped after 20 subjects have been treated. Therefore, all analyses will be performed for these subjects only.

Section 1.2.2 of CTP: The Residual Effect Period (REP) of apremilast is four days. This is the period after the last dose with measurable drug levels and/or pharmacodynamic effects is still likely to be present.

The following study phases will be defined for the analysis of adverse events (AEs):

- **Screening**
 - Ranging from 0:00h on day of informed consent until administration time of apremilast in treatment period 1.
- **On treatment** (labelled “**Tfasted**”, “**Tfed**”, “**R1fasted**”, “**R1fed**”, “**R2fasted**”)
 - **EU-sourced Otezla fasted (“Tfasted”)**: Ranging from the time of administration of Otezla (EU source) in the fasted state until 4 days (96 h) thereafter OR until next administration of Otezla, whatever occurs first.
 - **EU-sourced Otezla fed (“Tfed”)**: Ranging from the time of administration of Otezla (EU source) in the fed state until 4 days (96 h) thereafter OR until next administration of Otezla, whatever occurs first.
 - **US-sourced Otezla fasted (“R1fasted”)**: Ranging from the time of administration of Otezla (US source) in the fasted state until 4 days (96 h) thereafter OR until next administration of Otezla, whatever occurs first.
 - **US-sourced Otezla fed (“R1fed”)**: Ranging from the time of administration of Otezla (US source) in the fed state until 4 days (96 h) thereafter OR until next administration of Otezla, whatever occurs first.
 - **Japan-sourced Otezla fasted (“R2fasted”)**: Ranging from the time of administration of Otezla (Japan source) in the fasted state until 4 days (96 h) thereafter OR until next administration of Otezla, whatever occurs first.
- **Follow-up** (labelled “**F/U Tfasted**”, “**F/U Tfed**”, “**F/U R1fasted**”, “**F/U R1fed**”, “**F/U R2fasted**”)
 - **F/U Tfasted**: Ranging from the end of REP Tfasted until the next administration of Otezla OR until trial termination, whatever occurs first.
 - **F/U Tfed**: Ranging from the end of REP Tfed until the next administration of Otezla OR until trial termination, whatever occurs first.
 - **F/U R1fasted**: Ranging from the end of REP R1fasted until the next administration of Otezla OR until trial termination, whatever occurs first.
 - **F/U R1fed**: Ranging from the end of REP R1fed until the next administration of Otezla OR until trial termination, whatever occurs first.
 - **F/U R2fasted**: Ranging from the end of REP R2fasted until the next administration of Otezla OR until trial termination, whatever occurs first.

Section 7.3.4 of the CTP: Note that AEs occurring after the last per protocol contact but entered before final database lock will be reported to Pharmacovigilance only and will not be captured in the trial database.

The following AE displays will be provided in the report:

A) Section 15.3 and Appendix 16.1.13.1.8 (for ClinicalTrials.gov and EudraCT only) of the CTR displays:

In these displays, the on treatment phase will be analysed (labelled with the name of the study treatment (short label)). Screening and follow-up periods will not be included in this analysis.

The following totals will be provided in addition (Section 15.3 only):

- a total over all on treatment phases included in this analysis ("Total")

B) Section 15.4 of the CTR displays:

- Screening
- On treatment (labelled with the name of the study treatment (short label))
- Follow-up phases (labelled “F/U Tfasted”, “F/U Tfed”, “F/U R1fasted”, “F/U R1fed”, “F/U R2fasted”)

For detailed information on the handling of the treatments refer to Technical TSAP ADS plan and Analysis Data Reviewers guide.

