1.2.2 Residual Effect Period

The Residual Effect Period (REP) of apremilast is four days. This is the period after the last dose with measurable drug levels and/or pharmacodynamic effects is still likely to be present.

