5.2.6.2 Adverse event collection and reporting

5.2.6.2.1 AE collection

Upon enrolment into a trial, the subject's baseline condition is assessed (for instance, by documentation of medical history/concomitant diagnoses), and relevant changes from baseline are noted subsequently.

Subjects will be required to report spontaneously any AEs as well as the time of onset, end time, and intensity of these events. In addition, each subject will be regularly assessed by the medical staff throughout the clinical trial and whenever the investigator deems necessary. As a minimum, subjects will be questioned for AEs (and concomitant therapies) at the time points indicated in the [Flow Chart](#). Assessment will be made using non-specific questions such as 'How do you feel?'. Specific questions will be asked wherever necessary in order to more precisely describe an AE.

A carefully written record of all AEs shall be kept by the investigator in charge of the trial. Records of AEs shall include data on the time of onset, end time, intensity of the event, and any treatment or action required for the event and its outcome.

The following must be collected and documented on the appropriate CRF(s) by the investigator:

- From signing the informed consent onwards until an individual subject's end of trial:
 - All AEs (serious and non-serious) and all AESIs
 - The only exception to this rule are AEs (serious and non-serious) and AESIs in Phase I trials in healthy volunteers, when subjects discontinue from the trial due to screening failures prior to administration of any trial medication. In these cases, the subjects' data must be collected at trial site but will not be entered in the CRF or trial database and will not be reported in the CTR.
- After the individual subject's end of trial:
 - The investigator does not need to actively monitor the subject for AEs but should only report any occurrence of cancer and related SAEs and related AESIs of which the investigator may become aware of by any means of communication, e.g. phone call. Those AEs should, however, not be reported in the CRF.

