7.3.4 Safety analyses

Safety will be analysed based on the assessments described in Section [2.2.2.2](#). All treated subjects (TS, refer to Section [7.2](#)) will be included in the safety analysis. Safety analyses will be descriptive in nature and based on BI standards. No hypothesis testing is planned.

For all analyses, the treatment actually administered (= treatment at onset) to the subject will be used (any deviations from the randomised treatment will be discussed in the minutes of the Report Planning Meeting).

Treatments will be compared in a descriptive way. Tabulations of frequencies/proportions will be used to evaluate categorical (qualitative) data, and tabulations of descriptive statistics will be used to analyse continuous (quantitative) data.

Measurements (such as ECG, vital signs, or laboratory parameters) or AEs will be assigned to treatments (see Section [4.1](#)) based on the actual treatment at the planned time of the measurement or on the recorded time of AE onset (concept of treatment emergent AEs). Therefore, measurements planned or AEs recorded prior to first intake of trial medication will be assigned to the screening period, those between first trial medication intake and end of REP (see Section [1.2.2](#)) will be assigned to the treatment period. Events occurring after the REP but prior to next intake or end of trial termination date will be assigned to 'follow-up'. In case of two or more treatments, the follow-up will be summarized according to the previous treatment. These assignments including the corresponding time intervals will be defined in detail in the TSAP. Note that AEs occurring after the last per protocol contact but entered before final database lock will be reported to Pharmacovigilance only and will not be captured in the trial database.

Additionally, further treatment intervals (analysing treatments) may be defined in the TSAP in order to provide summary statistics for time intervals, such as combined treatments, on-treatment totals, or periods without treatment effects (such as screening and follow-up intervals).

Proprietary confidential information © 2020 Boehringer Ingelheim International GmbH or one or more of its affiliated companies

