7.8.1 Adverse Events

AEs will be coded with the most recent version of MedDRA.

Unless otherwise specified, the analyses of AEs will be descriptive in nature. All analyses of AEs will be based on the number of subjects with AEs and NOT on the number of AEs. BI standards as presented in “Analysis and Presentation of Adverse Event Data from Clinical Trials – Display Template” [BI-KMED-BDS-HTG-0041] ([10](#)) and [BI-KMED-BDS-HTG-0066] ([11](#)) will be applied.

The analysis of AEs will be based on the concept of treatment emergent AEs. That means that all AEs will be assigned to ‘screening’, ‘on-treatment’ or ‘follow-up’ phases as defined in [Section 6.1](#). AEs will be analysed based on actual treatments, as defined in [Table 6.1: 1](#).

According to the CTP, adverse events of special interest (AESI) will be analysed:

Section 5.2.6.1.4 of the CTP: *For this trial, depression, mood changes, suicidal ideation, and suicidal behaviour/attempt are considered as AESIs.*

According to ICH E3 ([12](#)), in addition to deaths and serious adverse events, ‘other significant’ AEs need to be listed in the clinical trial report. These will be any non-serious adverse event that led to an action taken with study drug (e.g. discontinuation or dose reduced or interrupted).

An overall summary of AEs will be presented.

The frequency of subjects with AEs will be summarised by treatment, primary system organ class (SOC) and preferred term (PT). Separate tables will be provided for subjects with serious AEs, for subjects with drug-related AEs, for subjects with drug-related serious adverse events and for subjects with AESIs. In addition, the frequency of subjects with AEs will be summarised by treatment, worst intensity, SOC and PT.

The SOCs and PTs will be sorted by frequency (within SOC). The MedDRA version number will be displayed as a footnote in the respective output.

In addition, frequencies of subjects with non-serious AEs that had an incidence of > 5% for at least one treatment will be summarised by treatment, primary SOC and PT.

For disclosure of adverse events on EudraCT, additional information not included in a standard AE analysis will be performed. The following three entries will be created:

- Adverse Events per arm for disclosure on EudraCT
- Non-serious Adverse Events for disclosure on EudraCT
- Serious Adverse Events for disclosure on EudraCT

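### SAP 6.1 gives deaths and SAEs that start more than 96 h after a dose no stated route into the public SAE entry or the Section 15.3 totals

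*SAP*

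**What the plan says.** SAP 6.1 assigns every AE to screening, on treatment or follow-up. On treatment runs from each dose "until 4 days (96 h) thereafter OR until next administration of Otezla, whatever occurs first". The 96 h comes from Protocol 1.2.2: "The Residual Effect Period (REP) of apremilast is four days". Follow-up runs from the end of that window to the next dose or to trial termination.

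SAP 6.1 then defines two sets of AE displays. Set A is headed "Section 15.3 and Appendix 16.1.13.1.8 (for ClinicalTrials.gov and EudraCT only) of the CTR displays" and uses the on-treatment phases alone: "Screening and follow-up periods will not be included in this analysis". The only total offered in Section 15.3 is "a total over all on treatment phases included in this analysis". Set B, CTR Section 15.4, shows screening, on treatment and follow-up, with each follow-up column named after the preceding treatment.

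SAP 7.8.1 plans separate tables for SAEs, drug-related SAEs and AESIs, and three EudraCT entries (AEs per arm, non-serious AEs, serious AEs). It states no exception to the phase rule.

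In the protocol, section 5.2.6.2.1 collects all AEs, SAEs and AESIs "From signing the informed consent onwards until an individual subject's end of trial". Section 7.3.4 says of events after the residual effect period: "In case of two or more treatments, the follow-up will be summarized according to the previous treatment". It also has SAEs and AESIs listed separately.

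**The concern.** A window tied to the residual effect period is a sensible way to attribute ordinary AEs to one of five treatments. Deaths and SAEs are normally counted whatever their cause, and a reader of a public SAE table will usually take it to cover the time a subject was observed in the trial. Under set A, an SAE starting on the fifth day of a washout, or in the days between the last window and the end-of-trial visit, is in the database and in Section 15.4 but not in the disclosed SAE entry or the Section 15.3 total.

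Inferential PK analysis was dropped after early termination (SAP 4), so safety is a main part of what the abbreviated report conveys. With 20 treated subjects, one subject missing from an SAE count is 1/20 = 5% of the treated set.

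**Working it through.** **Reproducing the plan's figure.** Residual effect period of 4 days × 24 h = 96 h, as SAP 6.1 states.

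**Is the window reasonable for drug effects?** Protocol 1.2.1 gives a terminal half-life of about 9 h. 96 / 9 = 10.7 half-lives, and 0.5^10.7 leaves about 0.06% of the drug. The window is adequate for attributing drug-related AEs.

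**How much observed time is outside set A?** Inputs:
- five doses (Protocol 3.1);
- dose-to-dose interval w of at least 5 days (Protocol flow chart, footnote 7), with no stated maximum;
- end-of-trial visit on Day 5 to 11. With dosing on Day 1, Day d is (d − 1) days after the last dose, so e = 4 to 10 days;
- on-treatment window of 4 days per dose.

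For a subject who completes all five periods:
- time from first dose to end of trial = 4w + e
- follow-up time = 4(w − 4) + (e − 4)

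| w (days) | e (days) | total (days) | follow-up (days) | share |
|---|---|---|---|---|
| 5 (minimum) | 4 | 24 | 4 + 0 = 4 | 16.7% |
| 5 (minimum) | 10 | 30 | 4 + 6 = 10 | 33.3% |
| 7 (assumption) | 4 | 32 | 12 + 0 = 12 | 37.5% |
| 7 (assumption) | 10 | 38 | 12 + 6 = 18 | 47.4% |

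On-treatment time is 5 × 4 = 20 days in every row.

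**Where does an SAE with onset in follow-up appear?**

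| Place | Included? | Source |
|---|---|---|
| Trial database | Yes, to end of trial | Protocol 5.2.6.2.1 |
| CTR Section 15.4 | Yes, under preceding treatment | SAP 6.1 B |
| Separate SAE and AESI listings | Yes; no 96 h limit stated | Protocol 7.3.4 |
| CTR Section 15.3, including its total | No | SAP 6.1 A |
| Registry appendix 16.1.13.1.8 | No; no second route stated | SAP 6.1 A, SAP 7.8.1 |

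SAP 7.8.1 counts subjects rather than events, so a count falls short only when a subject's sole qualifying event starts in follow-up.

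**The case against.** The strongest defence is that the SAP does what the protocol asks. Protocol 7.3.4 adopts the treatment-emergent concept, separates the treatment period from follow-up and leaves the detail to the SAP. It does not say which CTR section must carry follow-up events. Section 15.4 presents them by preceding treatment, and the listings show them individually. A reader of the full report would find the event. This stands: there is no breach of the protocol and no loss from the report.

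Several stronger readings are tempting, but the documents do not support them:
- *A disclosed AESI count could wrongly read zero.* The three EudraCT entries in SAP 7.8.1 include none for AESIs. The AESI point is confined to the Section 15.3 table.
- *An SAE that stops the trial could vanish from disclosure.* Protocol 3.3.4.3 does make a drug-related SAE a stopping reason without a time limit, but the scenario is hypothetical. SAP 4 says the trial ended because the BI 730357 programme was terminated.
- *Anything first dated at the end-of-trial visit is excluded.* AEs are assigned by recorded onset, not by visit, and an early Day 5 visit can fall inside 96 h of the actual dose. A death from an event that began within the window also still counts as on treatment.
- *Up to a third of SAEs are missed.* The 17% to 33% is a share of days, not of events, and late drug-related events are unlikely at more than ten half-lives.

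Finally, SAP 6.1 and 7.8.1 refer to display standards and technical files that are not available here and may add detail. They could resolve the point, but the SAP's explicit rule currently points the other way.

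**Conclusion.** The point holds in a limited form. It is a cheap improvement, not an error in the analysis. SAP 6.1 A states a rule that keeps deaths and SAEs with onset beyond 96 h out of the public SAE entry and the Section 15.3 totals, and no exception or alternative route is given. The resulting counts can understate the number of subjects with an SAE after first dose. In Section 15.3 the same applies to AESIs.

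For a completer at the minimum washout, the uncovered share of time from first dose to end of trial is 17% to 33%. The 38% to 47% range applies only if washouts averaged 7 days, which is an assumption. The conclusion also rests on two readings: that the SAE and AESI tables of SAP 7.8.1 sit in Section 15.3, and that the EudraCT entries sit in the registry appendix. The SAP implies both without saying so table by table. The documents report no results, so whether any event falls in the gap is unknown.

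**What to change.** In SAP 6.1 A, keep the 96 h window for the general AE tables and make three additions:
1. In Appendix 16.1.13.1.8, include deaths and SAEs with onset from first dose to end of trial, labelling those with follow-up onset as follow-up under the preceding treatment.
2. In Section 15.3, add the same labelled follow-up columns to the SAE, drug-related SAE and AESI tables.
3. In those three tables, add a total covering all phases after first dose beside the on-treatment total.

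If the columns are not added, a footnote in both places should say that events with onset in follow-up are excluded and appear in Section 15.4.

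The cost is SAP wording and a few columns, because the follow-up phases are already derived for Section 15.4. The small downside is that late events unlikely to be drug effects will stand beside a treatment name; the follow-up label addresses this. Data collection does not change.
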